Official Title: Development of Mechanistically Informed Therapy for Task-Specific Dystonia Using Noninvasive Neuromodulation

Protocol#: Pro00094131

NCT#: NCT06422104

Document Date: 11/09/2023 (Version 1.31)

General Information

*Please enter the full title of your protocol:

Development of Mechanistically informed Therapy for Task-Specific Dystonia Using Noninvasive Neuromodulation

*Please enter the Short Title you would like to use to reference the study:

Neuromodulation Therapy for Task-Specific Dystonia

* This field allows you to enter an abbreviated version of the Study Title to quickly identify this study.

Standard Research Summary

Purpose of the Study

- Objectives & hypotheses to be tested

The overarching goal of this study is to develop a non-invasive neurostimulation therapy for patients with focal hand dystonia (FHD). Specifically, the data obtained from this study will determine if engaging the striatum during non-invasive brain stimulation in the form of Transmagnetic Stimulation (TMS) can provide prolonged improvement of dystonic symptoms. Previous work in this field has advanced our understanding of regional brain circuit disruptions in dystonia and shown some efficacy in improving focal dystonia using non-invasive brain stimulation, though as of yet the effects are relatively modest and not enduring.

Goal: To characterize baseline behavioral and structural differences between focal hand dystonia subjects and healthy volunteers and evaluate safety and feasibility of neurostimulation therapy.

Visit 1: 70 FHD subjects and 70 healthy volunteers (HV) will be recruited to provide writing samples on digital writing tablet at Duke Brain Stimulation Research Center (BSRC).

Visit 2: A small cohort of 70 FHD subjects and 70 HV from visit 1 will be recruited to undergo functional MRI brain at Duke Brain Imaging and Analysis Center (BIAC). Data from visit 2 will also be used to localize the cortical target for TMS stimulation in visits 3, 4 and 5. Overall, data from visits 1 and 2 will be used to establish baseline outcome measures for visits 3, 4 and 5.

A urine drug screen and pregnancy test prior to visits 3-5.

[figure not shown]
[figure not shown]

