Dystonia is an involuntary movement disorder characterized by sustained or intermittent muscle contractions causing abnormal postures that are patterned and associated with overflow of muscle activation(1). Writer's cramp is characterized by excessive, unintended muscle activation selectively occurring during the task of writing. Its prevalence is 6.9 per 100,000 persons. Thirty percent of subjects report economic problems and 21% report pain significantly impairing independence in activities of daily living and work(1–3). Currently no disease modifying therapies are available. Most effective symptomatic therapies include botulinum toxin to transiently paralyze the overactivated muscles. Such treatments require access to highly specialized practitioners to avoid causing impaired dexterity, exhibit waning effects over the 3-month treatment interval, and vary efficacy based on the complexity of an individual's dystonic movements. For WC subjects, the risk of invasive brain surgery modalities such as Deep Brain Stimulation is weighed against the severity of their symptoms and DBS therefore is rarely a viable option (4). As a result, there are currently no highly effective non-invasive treatment for writer's cramp. Improved efficacy, longer therapeutic duration, and ultimately curative therapies for writer's cramp dystonia are needed.

Converging lines of evidence from human subjects and rodent models of dystonia suggest that abnormal striatal plasticity appears to be a common feature(5–8). In normal healthy mice, the presence of long-term potentiation (LTP) and long term depression (LTD) leads to normal plasticity of excitatory corticostriatal synapses. In dystonia, alteration in striatal physiology is characterized by abnormal plasticity of enhanced LTP and absence of LTD at excitatory corticostriatal synapses in a DYT1 mouse model(9). In addition, last year one of my mentors [name] laboratory discovered that hypoactivity of a translational regulatory pathway was shared across three forms of dystonia, two inherited dystonias and one sporadic focal dystonia(10). The pathway, eIF2 α , had been previously described to regulate the threshold for establishing long term synaptic plasticity(11). The eIF2 α pathway impairments in dystonia predict excess LTP and impaired LTD, consistent with the DYT1 model observations.

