Visit 1: 70 HV and 70 FHD subjects will be recruited at the Duke BSRC in the Duke Main Hospital. After the study team consents the subject, the following will be obtained: Patient's medical history to evaluate appropriateness of dystonia diagnosis. Patient will also be asked about the symptoms and signs of dystonia on rating scales including Adult dystonia and disability rating scale (ADDS)(45) Burke Fahn Marsden Rating Scale (BFM) and Pain Scale.

Subjects will then be asked to perform 3 writing samples (WT-1, WT-2, and WT-3) and non-writing samples on a digital tablet. WT-1 will be a single sentence written repeatedly 10 times to quantify writing performance. WT-2 will be a different single sentence written 10 times. WT-3 will be a linguistically diverse paragraph. All writing tasks will be performed by subjects using their dominant **left or right hand**. All subjects will be videotaped from the neck down, focused on their arms and hands during the writing sampling to allow careful examination of subject's hand and finger movements for Writer's Cramp Rating Scale (WCRS)(46) by 2 expert physicians (one Duke physician and one external physician) blinded to the group identity.

The patients videos of writing assessments are reviewed by the research team to ensure no personal identifier information (face, name, DOB) is visible. Videos are then deidentified and an ID number is assigned to each video for blinding purposes. The research staff then imports the videos to a secure Duke server including DukeBox and Duke PACE environment. The external physician will only access the videos using the Duke PACE environment while the internal Duke physician may access the videos using either the Duke Neurology server, DukeBox or Duke PACE environment. The physicians will rate the participants' writing assessments using established dystonia rating scales (WCRS, BFM).

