Visit 2: 70 FHD subjects and 70 HV from visit 1 will be recruited to undergo a functional MRI brain at Duke BIAC. To assess patient's baseline, subjects will copy a sentence using their dystonic **left or right hand** in fMRI suite alternated by periods of rest using an MRI compatible digital tablet. Writing task and control motor task will be back-projected onto a screen located at the head of the MRI bed using an LCD projector. Subjects will view the screen via a mirror system located in the head coil. Task onset will be electronically synchronized with the MRI acquisition computer using Cigal computer software. Task administration and collection of writing data will be computer controlled. The scanning session will take about 1.5 hr and include structural MRI, DTI, Swan, resting state fMRI and task-based fMRI.

BOLD images will be acquired using a GE Premier Performance 3T MRI scanner, which is an improved version of GE's FDA-approved Premier system, but with better capabilities for high-resolution imaging. All operational parameters on this improved system will be within FDA guidelines to meet the same minimal risk device criteria and ensure safety of human subjects. As such, an Investigational Device Exemption (IDE) is not necessary. The research conducted under this protocol is not to evaluate the safety and efficacy of this device.

A urine drug screen and pregnancy test prior to visits 3-5.

Visits 3, 4 and 5: 5 healthy volunteers who completed visits 1 and 2 will be recruited to undergo development of TMS stimulation protocol at Duke BSRC. Following protocol development, 20 focal hand dystonia subjects who completed visits 1 and 2 will also be recruited to undergo TMS stimulation at Duke BSRC. All 25 subjects will undergo the procedure as detailed below:

[figure not shown]

Figure 3: Sequence of events for research visits 3, 4, and 5. A) Overview of TMS stimulation, writing assessment and fMRI imaging. B) TMS session will be divided into 4 blocks of writing, each 5 minutes.

1. MRI Brain images from visit 2 will be uploaded to a neuro-navigation system (Brainsight: Rogue Research, Montreal, Canada) at the Brain Stimulation Service Stimulation Service Center

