 5. Of note, although both writing task and writing assessment will comprise of a writing and non-writing sample on a digital tablet, writing assessment will additionally entail video recording of the subjects' writing from the neck down, focused on subjects' arms and hands. These recordings will be used to complete Writer's Cramp Rating Scale (WCRS)(46) and Adult dystonia and disability rating scale (ADDS)(45) by an observer blinded to treatment. Overall, writing task is different from writing assessment in that writing task will only be used as part of the investigational treatment while writing assessment will consist of outcomes measures data collected for analysis.
 6. Data from visits 3, 4 and 5 will be used to determine safety of TMS stimulation protocol and feasibility of writing task and fMRI with stimulation protocol.

Selection of Subjects

- List inclusion/exclusion criteria and how subjects will be identified.

Inclusion criteria:

Healthy Control Participants:

1. 18yrs and older
2. **Left or Right hand dominance**
3. Age-matched to Focal Hand dystonia patients
4. Must be able to sign informed consent

5. Must be literate

Focal Hand dystonia Patients:

1. 18yrs and older
2. **Left or Right hand dominance**
3. **Diagnosed with Writer's Cramp dystonia in left or right hand**
4. Must be able to sign informed consent
5. Must be literate

Exclusion criteria:

Healthy Control Participants and Focal Hand dystonia Patients (visit 1)

1. Other neurological movement disorders diagnoses including other types of dystonia, Parkinsonism, or essential tremor
2. Botulinum toxin injections within 3months of research study
3. Medications with effects on the central nervous system including anticholinergic, benzodiazepines, and muscle relaxants among others within 1 week of the study
4. No physical or occupational therapy of the upper extremities

Healthy Control Participants (visits 2-5) and Focal Hand dystonia Patients (visits 2-5):

1. Other neurological movement disorders diagnoses including other types of dystonia, Parkinsonism, or essential tremor
2. Botulinum toxin injections within 3months of research study
3. Medications with effects on the central nervous system including anticholinergic, benzodiazepines, and muscle relaxants among others within 1 week of the study
4. No physical or occupational therapy of the upper extremities
5. Any contraindications to MRI (ie: metal in body or implanted medical devices, etc)

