Our preliminary analysis of the Duke patient population reveals sufficient population of FHD subjects to recruit for our study at Duke University. Our electronic patient database identifies 186 Duke patients with a specific diagnosis of organic writer's cramp (ICD 9 code 333.84). Because ICD 10 code does not have a specific writer's cramp diagnosis, we suspect that more cases are included within the ICD G24.9 (focal dystonia) group. Therefore, the primary care providers for all 837 subjects with either of these codes may be contacted by research coordinator for patient candidacy for this research study as detailed in Section 6 eIRB submission form.

Analysis and Statistics: [name] in the Department of Neurology, **[name] and [name] in the BERD core of the Statistics Department** will be **involved** the de-identified data **analysis** but will be not involved in collecting the data. Visit 1 data of handwriting metric differences between healthy participants and focal hand dystonia patients will establish writing metric sensitivity at our site and recalculate power analysis to adjust cohort sizes, or improve technique, as indicated for visits 2, 3, and 4. For Visit **3 -5**, a two-way ANOVA will be performed with groups (healthy vs dystonia) and stimulation type (task during vs after stimulation) as the main factor within subjects. A two-way repeated measures ANOVA will be conducted with stimulation type (task during vs after stimulation) and treatment type (sham vs active) as the main factors between subjects for each handwriting measure.

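### The writing hand is defined as dominant at Visit 1, dystonic at Visit 2 and not at all at Visits 3-5, so a patient whose affected hand is not dominant could be measured on an unaffected hand at Visit 1.

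*Combined protocol and SAP*

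**What the plan says.** Four parts of the protocol bear on which hand writes.

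- **Design & Procedures, Visit 1** (70 patients, 70 healthy volunteers): "All writing tasks will be performed by subjects using their dominant" hand, left or right. These samples supply the tablet metrics, and the videos are scored by two physicians blinded to group.
- **Design & Procedures, Visit 2** (again 70 and 70): in the scanner "subjects will copy a sentence using their dystonic" hand, left or right. No separate instruction is given for healthy volunteers.
- **Visits 3, 4 and 5** (Purpose of the Study, and steps 3 to 5 of Design & Procedures): a writing task during stimulation and a writing assessment before and after it. No hand is named. Step 2 records the muscle response contralaterally and allows motor threshold to be set in one or both hemispheres, so it does not settle the hand either.
- **Selection of Subjects**: patients qualify with "Left or Right hand dominance" and, as a separate criterion, "Diagnosed with Writer's Cramp dystonia in left or right hand". No inclusion or exclusion criterion links the two.

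The data have two downstream uses. Purpose of the Study says that information from Visits 1 and 2 "will be used to establish baseline outcome measures for visits 3, 4 and 5". Data Analysis & Statistical Considerations says that the Visit 1 difference between patients and healthy participants "will establish writing metric sensitivity at our site and recalculate power analysis to adjust cohort sizes".

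**The concern.** Two different hand rules feed one baseline, and eligibility does not guarantee that they pick out the same hand. A right-handed patient with writer's cramp only in the left hand meets every stated criterion. Under the text as written, that patient writes with the right hand at Visit 1 and the left hand at Visit 2.

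Three things would follow for such a patient. The Visit 1 metrics and ratings would describe a hand without dystonia and pull the patient mean towards the healthy mean. Visit 1 handwriting would not correspond to the Visit 2 task. And nothing would flag the mismatch: raters blinded to group would properly score the hand as normal, and the plan does not ask for affected versus dominant side to be kept as an analysis variable.

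Separately, and however common such patients are, the healthy volunteers' writing hand at Visit 2 is undefined, although comparing the two groups at baseline is part of the stated goal.

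**Working it through.** **Step 1. Compare the rules by type of participant.**

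| Participant | Visit 1 | Visit 2 | Visits 3-5 |
|---|---|---|---|
| Patient, dominant hand affected | affected hand | affected hand | not stated |
| Patient, only non-dominant hand affected | unaffected hand | affected hand | not stated |
| Healthy volunteer | dominant hand | rule cannot be applied | not stated |

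The first row is consistent across Visits 1 and 2. The second row is the problem case. The third row is a gap regardless of who enrols.

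**Step 2. Is the second row possible?** Yes. Dominance and affected side are separate criteria, and none of the exclusions removes a discordant patient. Whether any such patient has enrolled, or will, cannot be read from the documents.

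**Step 3. What would it do to the Visit 1 comparison?** The protocol gives no target difference, standard deviation or power for that comparison, so there is no figure of its own to reproduce. What follows is illustration only.

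Inputs:
- 70 per group (protocol).
- Two-sided 5% two-sample t-test (assumed; the protocol gives alpha 0.05 but does not tie it to this comparison).
- Share q of discordant patients (assumed; not in the documents).
- The unaffected hand performs like a healthy volunteer's dominant hand (assumed).

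The difference detectable with 80% power at 70 per group is d = 0.477 SD. If a share q contributes no difference, the expected difference is d(1 - q). The non-centrality is d(1 - q) × √(70/2), on 138 degrees of freedom. The sample needed to keep 80% power grows by 1/(1 - q)².

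| q | Patients of 70 | d(1 - q) | Power | Sample factor |
|---|---|---|---|---|
| 0% | 0 | 0.477 | 80% | 1.00 |
| 2% | 1.4 | 0.467 | 78% | 1.04 |
| 5% | 3.5 | 0.453 | 76% | 1.11 |
| 10% | 7 | 0.429 | 71% | 1.23 |
| 20% | 14 | 0.382 | 61% | 1.56 |

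Mixing two kinds of patient also adds q(1 - q)d² to the patient variance. At q = 20% this is 0.2 × 0.8 × 0.477² = 0.036, which lowers power only from 61% to 60%, so the table leaves it out.

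**Step 4. Does it reach the stimulation results?** Each stimulation block has its own writing assessment before and after. The pre/post change within a visit therefore does not use Visit 1 handwriting. The hand at those visits still needs to be stated.

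**The case against.** The best defence is that the two words were meant to name the same hand. The protocol requires writer's cramp specifically and describes it as "excessive, unintended muscle activation selectively occurring during the task of writing". A person normally has that problem in the hand they write with, which is normally the dominant one. The reference to left or right recurs in the Visit 1, Visit 2 and inclusion text, which would fit a single intention to admit left-handers. This is a plausible account of what was meant, and it is why the discordant share may be small or zero. It does not make the text consistent: staff following the Visit 1 sentence would use the dominant hand whatever the affected side, and the volunteers' hand at Visit 2 stays undefined.

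A second objection is that the power figures rest on invented shares and on a 0.477 SD difference that the protocol never targets. That is correct, and they are offered only as a scale that starts at zero. The 70 patients are justified in the protocol by screening failure ahead of a pilot cohort of 20, not by a Visit 1 test.

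A third is that a diluted difference would push the recalculated cohort upwards, the cautious direction. That also stands, although the estimate of how sensitive the writing metrics are would still be wrong.

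A reader might infer that some patients' baselines are in fact taken from a healthy hand, or that the active-versus-sham comparison is biased. The documents support neither. They permit a discordant patient but report none. The Visit 2 task already uses the dystonic hand in patients, and Visits 3-5 carry their own pre-stimulation assessment.

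**Conclusion.** The inconsistency is real and can be read directly from the text: three different treatments of the writing hand across five visits, one of which cannot apply to half the participants at Visit 2, and no eligibility criterion that makes the difference harmless.

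The consequence is conditional. If no patient is affected only in the non-dominant hand, the Visit 1 comparison loses nothing. At one or two such patients in 70 the loss is negligible, and it becomes material only at shares around 10% or more. That scale assumes that the unaffected hand writes like a control's.

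The exposure is confined to Visit 1 handwriting and ratings, their correspondence with Visit 2, and the power recalculation that uses them. The case for acting rests on the contradiction and the low cost of removing it, not on the larger scenarios.

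**What to change.** State one data-collection rule for Visits 1 to 5: patients write with the hand affected by writer's cramp, and healthy volunteers write with their dominant hand. Put it in the Visit 1 and Visit 2 paragraphs of Design & Procedures and in the Visits 3-5 text there and in Purpose of the Study.

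Record dominant hand and affected hand for every patient, including those already seen at Visit 1; the sample size section mentions preliminary writing data from 30 subjects. Present the Visit 1-2 comparison with healthy volunteers both with and without any discordant patients. Under the single rule such patients would write with a non-dominant hand against controls' dominant hands, so dominance would be mixed with disease.

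The cost is a sentence or so in each place and two recorded fields. The downside is small: Visit 1 data already collected from any discordant patient were taken under the dominant-hand rule and must be flagged as such.

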Visit 3, 4 and 5: 5 HV who completed visits 1 and 2 will be recruited to undergo development of TMS stimulation protocol at Duke BSRC. TMS Stimulation will be provided up to 20 minutes (at 10Hz) with a writing sample during stimulation. Subjects will also perform a writing assessment before and after each stimulation block. An fMRI will be performed after completion of each TMS stimulation session.

20 focal hand dystonia subjects who completed visits 1 and 2 will also be recruited to undergo 3 visits of TMS stimulation at Duke Brain Stimulation Center. The 3 visits will each be 1 week apart. 2 visits will involve active TMS and 1 visit will be sham TMS. During one of the active TMS visits, TMS coil will be applied to the premotor cortex for brain stimulation while during the other active TMS visit, TMS coil will be applied to the primary sensory cortex. TMS stimulation protocol will consist of 10Hz stimulation for up to 20 minutes with a writing task during the stimulation block. Subjects will undergo a writing assessment before and after each stimulation block and complete TMS side effects survey. Writing task is different from writing assessment in that writing task will only be used as part of the investigational therapy while writing assessment will be data collected for outcomes measures. fMRI will be performed after completion of each of the 3 TMS visits.

Background & Significance

- Should support the scientific aims of the research

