 3. Healthy volunteers will undergo TMS stimulation protocol development. Subjects will receive 10Hz active stimulation at premotor cortex during one visit and primary sensory cortex during another visit for up to 20 minutes with stimulation intensity up to 120% of resting motor threshold which is within the published safety guidelines (47) and based on previously published protocol used in multiple human studies(13–16). The resting motor threshold is a baseline stimulation intensity determined using the protocol in step 2. Additional stimulation parameters including duration of continuous stimulation, interstimulus interval, stimulation intensity, orientation of magnetic coil, biphasic or monophasic stimulation will be developed with healthy volunteers based on the published safety guidelines(47), writing assessment (includes writing and non-writing sampling) and feasibility within 20 minutes stimulation paradigm.
 4. WC subjects will undergo TMS stimulation visits 3, 4 and 5. 2 visits will include active TMS stimulation while the remaining one visit will be a control sham stimulation. Of the 2 active TMS stimulation visits, subjects will receive TMS at premotor cortex during one visit and at primary sensory cortex during the other active TMS visit. The dosage of active stimulation will be 10Hz for up to 20 minutes with resting motor threshold up to 120% which is within the published safety guidelines (47) and based on previously published protocol used in multiple human studies(13–16). During both active and sham stimulation blocks, subjects will be asked to perform a writing task of writing a diverse paragraph as an online stimulation task. The stimulation block will be preceded and followed by a writing assessment and TMS acute side effects survey to assess safety of the stimulation. Visit 3, 4, and 5 will occur 1 week apart. Subject will undergo fMRI after each of the 3 TMS visits.

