The most commonly reported side effect of rTMS is headache. This headache is typically of a muscle-tension type. It usually develops during or immediately after the stimulation and may last for minutes to hours following the end of the stimulation. It is typically limited to the day of stimulation, and usually responds promptly to single doses of over the counter pain medications. Neck pain or scalp pain may also occur. Both are usually managed easily with over-the-counter analgesics. Participants may take Advil or Tylenol to reduce discomfort. Tylenol or Advil will be used according to recommended dosage, ensuring that the participant has no allergies and has not taken other NSAIDS or acetaminophen. Liver damage can occur when more than 4,000 mg of acetaminophen are taken in 24 hours or when taken with alcohol. Ibuprofen can cause stomach bleeding in certain individuals or when not adhering to dosage recommendations. Once the Advil or Tylenol has had time to take effect, we will resume stimulation. If there is still discomfort, topical lidocaine cream may be applied to the area of the scalp where stimulation occurs. Topical lidocaine has been shown to relieve discomfort resulting from rTMS for some people. Topical lidocaine should not be used on large areas or on cut, irritated or swollen skin. Twenty minutes must be allowed for the lidocaine cream to take effect. If implemented, Tylenol, Advil, and lidocaine cream will be used as directed.

As noted in Rossi et al(47), Loo and colleagues reported mild and transient changes in auditory threshold in two depressed patients following a 2-4 week rTMS course of rTMS. Cases of tinnitus have been reported after rTMS treatments. In addition, recently in a study investigating the effects of rTMS on symptoms of depression, a patient experienced moderate to severe tinnitus after an rTMS session in which earplugs were not used. Rossi et al. recommended that hearing protection always should be worn during rTMS application, and that individuals with cochlear implants not receive rTMS. In the current study, earplugs will be worn by all subjects during rTMS procedures. Individuals with cochlear implants will be excluded from participation.

Illicit drugs such as cocaine can reduce the seizure threshold. As a result, all subjects will undergo urine toxicology test prior to each TMS session and positive subjects will be excluded from the study. Risks to the unborn children of

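### The side-effects survey is described only before and after the stimulation block, so it cannot measure symptom duration and can miss late or already treated symptoms

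*Combined protocol and SAP*

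**What the plan says.** Evaluating safety is part of the goal in Purpose of the Study, and step 6 of Design & Procedures (Visits 3, 4 and 5) repeats it: "Data from visits 3, 4 and 5 will be used to determine safety of TMS stimulation protocol".

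The instrument is a survey tied to the stimulation block. Step 4 says: "The stimulation block will be preceded and followed by a writing assessment and TMS acute side effects survey to assess safety of the stimulation". The summary in Purpose of the Study agrees: "Subjects will undergo a writing assessment before and after each stimulation block and complete TMS side effects survey". Neither place gives a clock time, a recall window or a later administration. The three TMS visits are a week apart, and an fMRI follows each one. No survey is attached to the fMRI, and no safety follow-up is described after the last TMS visit.

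The TMS Adverse Events Plan (Risk/Benefit Assessment) describes the expected symptoms. "The most commonly reported side effect of rTMS is headache". On its course: "It usually develops during or immediately after the stimulation and may last for minutes to hours following the end of the stimulation", and "It is typically limited to the day of stimulation". The plan allows over-the-counter pain relief during a session, and then: "Once the Advil or Tylenol has had time to take effect, we will resume stimulation". If discomfort remains, a topical anaesthetic may be applied, with a twenty-minute wait. Nothing in the text says that the symptom, the relief given or its time becomes part of the safety data.

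**The concern.** The survey measures symptoms at two moments around the block, while the protocol's own account of headache runs past the second moment and allows it to be treated before then. Four kinds of information are exposed: how long a symptom lasted, whether it worsened later, whether a new one began after the subject left, and whether one was present but relieved by the time of the post-block survey.

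This matters because the survey is the only structured source for one of the study's stated aims. The other monitoring, under Data & Safety Monitoring, is general observation by the experimenter and expedited reporting of serious adverse events. A headache at home that evening is neither observed nor serious, so neither route would capture it. With 20 dystonia subjects in the TMS stage, a few unrecorded events would visibly change a reported rate, and they cannot be recovered reliably afterwards.

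**Working it through.** The documents state no headache rate, no share of symptoms expected after the survey and no sample-size reasoning for safety. There is no figure of the plan's own to reproduce, so the check is mainly a comparison of the survey's timing with the described course of symptoms.

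**Survey against symptom course**

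- *Onset during or just after stimulation, untreated, still present.* The post-block survey records it. The protocol calls this onset usual.
- *Same onset, lasting hours.* The survey records its presence. It cannot record duration or later worsening, because it is completed before these are known.
- *Onset later that day.* No later survey is described. The pre-block survey a week later could recover it only through a recall question, and none is specified. Because headache is typically confined to the day of stimulation, a question about current symptoms a week later would miss it.
- *Onset in the session, relieved, stimulation then resumed.* The post-block survey follows the relief. If it asks about symptoms at any time in the session, the event is captured. If it asks only about the present, the event can be missed or recorded as milder. The survey wording is not given.
- *Any late symptom after the last TMS visit.* There is no later pre-block survey. For dystonia subjects this is 20 of 20 × 3 = 60 sessions, one third. The order of active and sham visits is not stated, so some of these last sessions may be sham.

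**What an undercount would look like (assumed values only)**

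Take n = 20 dystonia subjects, since the survey is described in the step for them. Let p be the share who truly have headache and f the share of those the survey misses. Neither is in the documents. The expected recorded count is n × p × (1 − f).

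| p | true count | f = 0 | f = 10% | f = 25% | f = 50% |
|---|---|---|---|---|---|
| 10% | 2 | 2 | 1.8 | 1.5 | 1 |
| 20% | 4 | 4 | 3.6 | 3.0 | 2 |
| 30% | 6 | 6 | 5.4 | 4.5 | 3 |
| 40% | 8 | 8 | 7.2 | 6.0 | 4 |

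For example, 20 × 0.20 × (1 − 0.25) = 3.0.

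The chance that the survey records no headache at all is (1 − p(1 − f))^20. At p = 10% this is 0.90^20 = 12.2% when f = 0, and 0.95^20 = 35.8% when f = 50%.

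The column f = 0 is a real possibility: it holds if every headache has begun by the survey and is reported there.

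**The case against.** The strongest objection is that duration does not cause undercounting. A headache that lasts for hours is more likely, not less, to be present at a post-block survey, and the protocol puts usual onset inside the window that the survey covers. This stands. A reader might infer that the safety result undercounts headache because headache can last for hours; the documents do not support that. They also do not say that headache always lasts for hours, or that the survey is completed at once after the block. The text gives only the order of events, and Figure 3, which shows the sequence at these visits, is not reproduced in the copy reviewed.

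A reader might also infer that subjects have no contact with the study after their last stimulation. That goes too far: an fMRI follows every TMS visit, including the last, with staff who monitor for distress and an intercom to the investigators. The Data Analysis section also lists a Pain Scale for comparing baseline symptoms before and after visits. It stands among the dystonia symptom scales and is not described as a side-effect measure, so it does not close the gap.

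A third tempting inference is that the active-versus-sham difference in side effects is biased toward zero because relief is used mainly in active sessions. The documents say nothing about how relief is distributed, and the planned sham-versus-active ANOVA is for handwriting measures. No such comparison of side effects is planned, so no bias in one can be asserted.

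Finally, this is a pilot, the instrument is named an acute survey, and the expected effects are described as easily managed. That limits the severity. It does not answer the point that safety is a stated aim and that duration, late onset and treated symptoms have no described place in the data. The tinnitus statement, "Cases of tinnitus have been reported after rTMS treatments", adds little, since it gives no time of onset.

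**Conclusion.** The point holds as a limit on what the survey can show. As described, it should catch many headaches. It cannot measure duration or later worsening, and it can miss symptoms that begin later or are masked by relief given in the session. No safety follow-up is described after the last TMS visit.

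The size of any undercount cannot be derived from the documents and may be zero. The counts above rest on assumed values of p and f and serve only to show that, with 20 subjects, a difference of one to four recorded cases is within the range tried. The masking point depends on the survey's wording, which is not given; a question covering the whole session would remove most of it. The late-onset and duration points remain unless a later administration or recall item exists in material not seen here.

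This is a gap in data collection that should be closed before the TMS visits. It is not evidence that the safety result is wrong.

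**What to change.** Keep the pre-block and post-block surveys and state their timing and recall window. Then:

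1. Repeat the same survey after the fMRI already planned for each TMS visit. The text does not say how long after stimulation the scan takes place, so record the time of each survey.
2. At the start of the next visit, add a recall item: symptoms since the last session, onset, duration and medication taken.
3. Make one brief remote contact after the last TMS visit, with the same recall item.
4. Record any in-session symptom and the relief given, with its time. The entry must not delay or change relief; it can be made once the subject has been attended to.
5. Report the worst score from any time point against the pre-block score, by stimulation condition (premotor, primary sensory, sham), together with use of relief.

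The cost is a few minutes of an existing questionnaire per visit and one remote contact per subject. Reported side-effect rates may look slightly less favourable, because more is being asked. No change to clinical management is proposed.
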